Patients that are not willing to participate in the RCT, but do take part in the ancillary patient preference observational study, will have a baseline visit with a limited set of evaluations. At the baseline visit, age, sex, medication, age at onset of PD, duration of PD, Hoehn and Yahr stage, and comorbidities will be recorded. The patients will have an assessment of the patient-reported perceived quality of life (PDQ-39) and will fill in a questionnaire on preference for treatment and expectations (PROADP). Follow-up visits are planned at 9 months, 12 months, 24 months and 36 months after the study treatment. In these visits, the PDQ-39 and patient satisfaction with the treatment will be assessed (PROADP), complications and adverse events will be evaluated using a questionnaire and the medical charts will be reviewed for complications and adverse events. If necessary, based on complications and adverse events questionnaire, the medical information from other hospitals will be requested and reviewed. The first year of follow-up, a margin of one month is deemed acceptable in planning a visit, for the second and third year of follow-up, the visits will be completed within two months of the defined follow-up date.

Furthermore, during the study current preferences regarding treatment of advanced PD amongst treating physicians will be evaluated.

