12.4 Assessment schedules

	Visit 1 Baseline	Visit 2	Visit	Visit 4	Visit 5	Visit 6	Visit	Visit 8
	Daseille	1wk	3mo	6mo	9mo	12mo	, 24mo	36mo
Baseline characteristics	X							
EKG, CT/MRI brain	X							
blood analysis	Х					Х		
Medication	Х	Х	Х	Х	Х	Х	Х	Х
MDS-UPDRS motor score	Х					Х		
Clinical Dyskinesia Rating Scale (CDRS)	Х					Х		
Motor symptom diary (3 days)	X					Χ	Χ	Х
Non-motor symptom checklist	Χ					Х	X	Х
Impulsive compulsive (QUIP)	Χ					Х		
Apathy scale Starkstein (AS)	X					Х		
Neuropsychological examination (incl. Mattis Dementia rating scale)	X					X		X
Mini-International Neuropsychiatric Interview	Х					Χ		
Psychiatric assessment	X					Х		
Hoehn and Yahr stage	X					X	Χ	Х
AMC disability scale (ALDS)	X					Х	X	Х
PDQ-39	X				Х	Х	X	X
EQ-5D	X	X	Х	Х	Х	Х	X	X
Treatment preference	X							
Treatment satisfaction						Х	Х	Х
Satisfaction with life scale	Х					Х	Х	X
Treatment failures		X	Х	Х	Х	Х	Х	Х
Side effects/adverse events/complications		X	X	Х	Х	Х	X	Х
Crossover to other treatment			Х	Х	Х	Х	Х	X
iMTA Medical Consumption Questionnaire (iMCQ)	X		X	X	Х	X	X	Х
iMTA Productivity Cost Questionnaire (iPCQ)	X		X	X	Х	Х	X	X
Use of (informal) care	Χ		X	X	X	X	Х	Х
Caregiver burden	Х		Χ	Χ	Χ	Χ	Х	X

Version 7: 23-10-2019 43 of 48

Table 2: assessment schedule patient preference trial

	Visit 1 Baseline	Visit 2 9mo		Visit 4 24mo	Visit 5 36 mo
Baseline characteristics	Х				=
Medication	X	Х	Х	Х	X
Hoehn and Yahr stage	Х				
PDQ-39	Х		Х	Х	X
Treatment preference	Х				
Treatment satisfaction			Х	Х	X
Side effects/adverse events/complications		Х	Х	Х	X
Treatment failures and cross-over		Х	Х	Х	X

Version 7: 23-10-2019 44 of 48

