Certain outcomes were not part of the principal analyses. They will only be addressed in the main publication at the discretion of the reviewer and will be published separately otherwise. This applies to the following outcomes: functional health status (Hoehn & Yahr stage), non-motor symptoms (Non-Motor Symptom Checklist), laboratory measurements (levels of vitamin B6, B12 and folic acid), extensive neuropsychological assessment, depression (Hamilton Depression Scale), anxiety (Hamilton Anxiety Scale), suicidality (Columbia Suicide Severity Rating Scale), patient satisfaction based on a study tailored questionnaire, and caregiver burden based on a standardized questionnaire.

Outcomes - ancillary patient preference cohort study

Outcomes for the ancillary patient preference cohort study were the change in quality of life (PDQ-39) from baseline to 12 months after initiation of treatment; change in PD-medication expressed in LEDD from baseline to 12 months (including the continuous intrajejunal delivered levodopa); change in functional health status (ALDS) from baseline to 12 months; (S)AEs; stopping treatment; and switch to the alternative treatment after initially receiving the allocated treatment (*i.e.*, switch from DBS to CLI or vice versa).

Statistical analysis

General principles

The analyses were performed after completing the last 12-month follow-up visit, monitoring and data validation, and after submission of this SAP and HEAP to the medical ethics board and uploading of the SAP to the registration page of the study at www.clinicaltrials.gov. Analyses were performed by the investigators of the INVEST study group, independent of study sponsors, using SPSS statistics software (IBM Corp., Armonk, NY, USA) and Microsoft Excel for visualization of results.

No interim analyses were performed. Statistical uncertainty was expressed in two-sided 95% confidence intervals (CI). The main clinical outcome was viewed as significantly different between the CLI treatment RCT group and DBS treatment RCT group, if the two-sided P-value was less than 0.05. For other outcomes, no individual P-values were reported. In case of a non-normal distribution of one of the variables in a specific analysis in the RCT, that analysis was performed with bias corrected

accelerated bootstrapping, drawing 2,500 samples of the same sizes as the original samples and with replacement.

Patient flow diagram

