According to the Consolidated Standards of Reporting Trials 2010 statement (CONSORT), a flow diagram illustrating the number of participants ineligible, eligible, consented, randomized, received allocated treatment, excluded, withdrawn and lost to follow-up for the primary outcome was provided. Please see the Figure SAP-1 on page 29.

Analysis populations

Modified intention-to-treat population

The primary analysis consisted of the modified intention-to-treat (mITT) population which included all randomized patients who received the allocated treatment, regardless of continuation of treatment. Analyses in the original ITT population including all randomized patients, regardless of the treatment they had actually received (*i.e.*, also patients not receiving the allocated treatment and patients quitting study participation immediately after randomization) were accounted for in sensitivity analyses (see page 12, “Sensitivity analysis”) and were presented in the supplements.

As-treated population

To provide insight in potential bias resulting from excluding patients who did not adhere to the allocated treatment or switched treatment, analyses were additionally performed in an as-treated population categorizing the randomized patients according to the actual treatment(s) they were receiving at the moment of the 12-month visit (if available).⁷

Per protocol population

The per protocol population consisted of all patients receiving the allocated treatment who completed the study protocol without protocol violations.

Ancillary patient preference population

The ancillary patient preference population consisted of all patients who signed informed consent for this element of the study, started the chosen treatment and underwent at least the baseline visit and one follow-up visit. Patients were allowed to participate in the ancillary patient preference cohort study after withdrawal of consent for the RCT prior to randomization. Please see also Appendix II for the flowchart of the Ancillary patient preference cohort.

Adherence and protocol deviations and violations

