The difference between both treatment groups in the mean change from baseline to 12 months in total MDS-UPDRS part II and III was shown with 95% CI. Similarly, the difference between groups in mean change from baseline to 12 months in CDRS was shown, as well as the difference in mean change in total time in both off-drug state and on-drug state without bothersome dyskinesias as reported in the 3-day motor diary, the difference in mean change in usage of dopaminergic medication (LEDD), and ALDS in on-drug phase, all with 95% CI. Discontinuation of the allocated treatment or switch to the other treatment option were summarized using simple descriptive statistics. The change in cognition expressed in points on PD-CRS from baseline to 12 months was reported. For apathy, the numbers and frequencies of patients with apathy at baseline and after 12 months follow-up were shown. Moreover, the numbers and frequencies of patients who had developed apathy after 12 months (*i.e.*, no apathy at baseline, but presence of apathy after 12 months), was reported for both groups, including the difference between these frequencies and 95% CI. Similarly, numbers and frequencies of impulsive-compulsive disorders and, separately, of development of impulsive-compulsive disorders were shown, with difference and 95% CI of the latter. Additionally, the numbers and frequencies of resolution of impulse control disorders were reported for both groups as well as the difference and 95% CI. Psychiatric diagnoses were reported analogues to impulse-compulsive disorders.

The number of patients that would recommend their treatment at 12 months to others was reported and the difference in frequency between the treatment groups was reported with 95% CI.

We presented line listing of safety outcomes using counts and percentages. All (S)AEs, including death were reported for each treatment arm. See Table SAP3 for an overview of (S)AEs. The treatment course per group was expressed in number of patients stopping allocated treatment and number of patients switching to the alternative treatment.

Table SAP2. Main and secondary clinical outcomes at 12 months, mITT RCT population

Part A: continuous outcomes

Outcome	Within-treatment Change from Baseline to 12 Months								Between-Group Difference in Change from Baseline mean (95% CI)	P-value
	Baseline				Months					
	CLI		DBS		CLI		DBS			
no. of patients	mean ±SE	no. of patients	mean ±SE	no. of patients	mean ±SE	no. of patients	mean ±SE			

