CLI: continuous intrajejunal levodopa infusion, DBS: deep brain stimulation, RCT: randomized controlled trial, SAE: serious adverse event

Ancillary patient preference observational study arms

For both the observational CLI and DBS groups, changes in outcomes from baseline to 12 months after start of treatment were displayed in Table SAP4. The numbers of patients who stopped their advanced treatment and who switched between advanced treatments were reported.

To assess the extent of external validity of the mITT population, differences in baseline characteristics of all randomized patients (*i.e.*, both the CLI and DBS groups combined) and the separate observational (*i.e.*, non-randomized) CLI group and DBS group of the ancillary patient preference study were shown with 95% CI in supplementary Table SAP1-S. With regard to the main clinical outcome (the change in PDQ-39 summary index scores at 12 months relative to baseline), the difference between patients randomized to CLI treatment (mITT population) and those who preferred that treatment was reported with 95% CI. The same was done for patients randomized to DBS treatment (mITT population) and those who preferred that treatment. These figures were presented in the text.

To assess the impact of the treatment on the change in PDQ-39 at 12 months relative to baseline with more power, this was analyzed using multivariable regression in the total group of patients (*i.e.*, both the mITT randomized population and non-randomized population), taking into account significant imbalanced baseline variables and participation in the RCT or preference observational study.

Table SAP4. Ancillary patient preference observational study arms, outcomes at 12 months.

Outcome	Baseline				Within-treatment Change from Baseline to 12 Months			
	CLI		DBS		CLI		DBS	
	no. of patients	mean±SE	no. of patients	mean±SE	no. of patients	mean±SE or n (%)	no. of patients	mean±SE or n (%)
Main clinical outcome PDQ-39 summary index score								
Secondary outcomes LEDD (mg per day) ALDS score in on-phase								

ALDS: Amsterdam Linear Disability Scale, CLI: continuous intrajejunal levodopa infusion, DBS: deep brain stimulation, LEDD: Levodopa Equivalent Daily Dose, PD-CRS: Parkinson's Disease Cognitive Rating Scale, PDQ-39: Parkinson's Disease Questionnaire-39, SE: standard error. For continuous variables, mean and Standard Error were reported, for dichotomous variables the number of patients (n) and percentage (%).

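### The SAP's only preference-arm population requires a follow-up visit, and the first is at month 9, so treated patients who die or leave before any visit fall outside the observational harms, stopping and switching results

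*SAP*

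**What the plan says.** SAP, Analysis populations, defines one population for the preference arms: patients who consented to this part of the study, "started the chosen treatment and underwent at least the baseline visit and one follow-up visit". No all-treated or safety population is defined for them.

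Protocol 7.3 gives the preference schedule: "Follow-up visits are planned at 9 months, 12 months, 24 months and 36 months after the study treatment". For the first year "a margin of one month is deemed acceptable in planning a visit". Protocol 12.4, "Table 2: assessment schedule patient preference trial", agrees: after baseline the next visit is at 9 months, and adverse events, treatment failures and cross-over are first ticked there.

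The SAP lists (S)AEs, stopping and switching among the outcomes of the preference cohort. In its section on the observational arms it adds: "The numbers of patients who stopped their advanced treatment and who switched between advanced treatments were reported". Table SAP3 prints deaths, hospital admissions and other events as n and % for CLI-observational and DBS-observational beside the two RCT columns. The text that leads to the table says: "All (S)AEs, including death were reported for each treatment arm".

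On the randomised side, the same section of the SAP defines the modified intention-to-treat (mITT) population as "all randomized patients who received the allocated treatment, regardless of continuation of treatment". RCT visits start at week 1 (Protocol 7.3), and RCT adverse events are recorded from the screening visit (Protocol 8.2.1).

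**The concern.** Read together, the population rule and the visit schedule mean that a treated preference patient must still be alive and in the study at about month 9 to be counted. The months before that visit contain the operation or tube placement and the first complications. A death table whose denominator is conditional on attending a visit after that period cannot show the deaths that came before it, and the neighbouring RCT columns are not conditioned in the same way.

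This matters for reading the harms. The protocol plans at least 120 preference patients against 66 randomised, so these arms would supply most of the safety experience. Protocol section 3 gives adverse events as one of the reasons for following them. Protocol 12.6 says that outcomes in the preference group gain interest if the RCT's efficiency results are indecisive. A reader who compares the columns of Table SAP3 could take a difference created by the entry rule for a real one.

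The SAP also gives reason to think that loss is not harmless. It reports that comorbidity reduced the completeness of follow-up, and it expects missing values to be missing not at random. Appendix I does call some unfollowed preference patients missing at random, but only those whose follow-up never started for logistic reasons.

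**Working it through.** **1. The plan's own figures for these arms.** Protocol 4.4 gives detectable PDQ-39 differences between preference and randomised patients (two-sided 0.05, power 80%, SD 15, 33 randomised per arm). The formula is SD × (z₀.₉₇₅ + z₀.₈₀) × √(1/n₁ + 1/n₂). For DBS with 108 preference patients: 15 × (1.960 + 0.842) × √(1/33 + 1/108) = 8.36, or 8.42 with the exact t-test; the protocol states 8.4. The other three cases (72, 72 and 48 preference patients) give 8.92, 8.92 and 9.62 by the exact t-test; the protocol states 8.9, 8.9 and 9.6. These figures reproduce and are not in dispute. The point is about who is counted.

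**2. The two entry rules side by side.**
- Preference arms: consent, treatment started, baseline visit and one follow-up visit, with the first such visit at month 9 (month 8 to 10 with the margin).
- Randomised arms: allocated treatment received. The SAP's synopsis of protocol development adds that the patient continued in the RCT after randomisation. No month-9 condition appears in either place.

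**3. Who is lost and who is not.**
- Dies before any follow-up visit: outside the preference population.
- Leaves the study before any follow-up visit: outside, with any harm, stop or switch that occurred.
- Stops or switches early but attends a later visit: inside, and the event is counted.
- Misses month 9 but attends month 12: inside.

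**4. Illustration for deaths.** Assume that deaths are spread evenly over 12 months. The share before the first qualifying visit is 9/12 = 75%, and 8/12 = 67% to 10/12 = 83% with the margin. With true 12-month mortality d and a visit at month 9, the reported proportion is 0.25d / (1 − 0.75d):
- d = 2%: 0.005 / 0.985 = 0.5%.
- d = 5%: 0.0125 / 0.9625 = 1.3%.

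**5. Illustration for stopping or switching.** Assume 10% early loss, a true stop-or-switch rate of 20%, and a share s of those lost who had the event. The reported rate is (0.20 − 0.10s) / 0.90:
- s = 20% (loss unrelated to the event): 20.0%, no bias.
- s = 50%: 16.7%.
- s = 100%: 11.1%.

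The mortality, early-loss and stop-or-switch rates in steps 4 and 5 are assumptions. The documents give none for these arms.

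**The case against.** The strongest reply is that exclusion from Table SAP3 is inferred. The observational columns carry no population label, and the SAP says that all (S)AEs including death were reported per arm. The protocol line-lists preference-arm events (8.2.1) and plans chart review, with records requested from other hospitals where needed (7.3). The Appendix II flowchart is not available here and may account for treated patients without a visit. Early deaths may therefore have been listed in practice. This stands as far as it goes, but none of these texts supplies another denominator. The chart review is described as part of the follow-up visits, the line listing is safety reporting rather than an analysis population, and a percentage in Table SAP3 needs a defined base. The only one defined excludes these patients.

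A reader might also infer more than the documents support:
- *That PDQ-39 is equally affected, because the mITT keeps early losses by imputation.* For deaths before month 9 the SAP uses no PDQ-39 score in the RCT either. Only living early dropouts differ, and this is secondary.
- *That stopping and switching must look lower.* Step 5 shows no bias when loss is unrelated to the event, and early stoppers who attend later are kept.
- *That 75% of deaths, or 18 of 120 or 27 of 180 patients, would be removed.* The 75% assumes a constant hazard. The patient counts come from 20% × 9/12 = 15%, where the 20% is the RCT's sample-size allowance. The preference cohort has a lighter burden (about 5 hours against 15, with telephone assessments), so that rate cannot be carried over.
- *That the main results are at risk.* The primary economic outcomes and the main clinical test use the randomised mITT population only.

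**Conclusion.** The concern holds as a defect in the population definition for ancillary results. As written, treated preference patients who die or leave before any follow-up visit are outside the only observational population, while their arms' deaths, (S)AEs, stopping and switching are reported. If that population is the base of the observational figures, deaths are under-counted whenever one occurs before the first visit. Other harms, stopping and switching are under-counted to the extent that early loss is related to them. The randomised columns have no month-9 condition, although the mITT definition has a retention phrase of its own, so the contrast is real but not absolute.

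The size cannot be computed from the documents. The 67% to 83% range illustrates deaths spread evenly over the year; it is not an estimate. The point should be settled before the observational harms are read beside the RCT arms, but it does not reach the primary economic analysis or the main clinical comparison.

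**What to change.** For Table SAP3 and for the stopping and switching counts, define the preference population as all patients who consented, had a baseline assessment and started the chosen treatment, with no follow-up-visit condition. Label the observational columns of Table SAP3 with this population.

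Obtain events before the first visit from the chart review already planned in Protocol 7.3, carried out for these patients whether or not a visit took place. Add the enquiry to treating physicians that the SAP describes for patients lost to follow-up (death and its cause, use of the allocated or the alternative treatment). Its wording refers to allocated treatment, so it should be extended explicitly to the preference arms.

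The visit condition may stay for change in PDQ-39, LEDD and ALDS. One sentence should state how many treated preference patients it removes and how living early dropouts are handled there compared with the mITT population.

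The cost is a SAP wording change, a small amount of chart review, and observational safety figures that may be slightly less favourable.

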After it proved challenging to include patients in other centers than the primary including hospital (Amsterdam UMC), the recruitment and consent procedure was adjusted twice to enhance inclusion in the ancillary patient preference observational arms in other participating centers. First, it was no longer obligatory to sign the informed consent form face-to-face with the researcher for eligible patients who did not consider participation in the RCT but were willing to be included in the ancillary patient preference observational arms (2016). Patients could return the informed consent form by mail as of then. Second, treating physicians from non-participating centers were also allowed to register patients for the ancillary patient preference observational arms, after which the research team contacted the patient and enrolled them if eligible (2019). Furthermore, to enhance recruitment in the RCT in other centers, treating physicians were contacted frequently and patients were informed through the Dutch Parkinson Society. This did not lead to protocol changes.

Concerning the primary outcome, the usage of the Parkinson's Disease Questionnaire-39 (PDQ-39) was operationalized as follows: the difference between the two treatment groups (*i.e.*, DBS and CLI) in change from baseline to 12 months on the PDQ-39 summary index score. The change (*i.e.*, from baseline to 12 months) on total PDQ-39 was chosen as this score displays alteration in disease related quality of life after instalment of the allocated treatment and therefore is largely independent of possible differences in baseline values in the relatively small populations. The PDQ-39 has been a frequently used outcome measure in clinical trials for PD.⁴⁻⁶ Use of repeated PDQ-39 measures was planned in the original design; a PDQ-39 assessment was planned at the nine months follow-up time-point to be able to pool data with a designed similar trial by another study group. Unfortunately, that study and planned international pooling of data never came into existence. Because there was a limited number of repeated PDQ-39 measurements (*i.e.*, at baseline, nine months, and 12 months follow-up), no major differences between both follow-up points were

expected. Also, up to 2016 the nine months visits proved incomplete with regard to the PDQ-39 assessments. Therefore, it was decided not to perform a repeated measurement assessment.

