Adherence to the intervention CLI treatment was defined as having the percutaneous endoscopic gastrostomy (PEG) tube placed and having continuous administration of levodopa by means of the CLI pump. Adherence to the intervention DBS treatment was defined as having the DBS system implanted and turned on. Study patients were able to make small adjustments to their CLI or DBS settings if permitted by their healthcare professionals, major changes to treatment regimens could only have been implemented by healthcare professionals. Therefore, adherence was expected to be very good. Continuation of treatment was regularly inquired during the planned visits.

Protocol deviations were quantified and projected per study group. Protocol deviations were defined as treatment, research activities or other procedures that diverged from the study protocol were considered to have had no significant consequences for interpretation of study outcomes. A protocol violation was defined as a divergence from the protocol that might significantly have impacted the completeness, accuracy, and/or reliability of the study data, was not in line with the consent form, or

might have impacted patients' safety, welfare or rights.^{16,17} In Appendix I possible protocol deviations and violations were elucidated. All protocol deviations were line-listed according to treatment group. In addition, the number and percentage of patients in each treatment group experiencing one or more protocol deviations were presented. Minor protocol deviations did not impact inclusion in all analyses. Protocol violations did not alter inclusion in the (modified) intention-to-treat analysis or the ancillary patient preference observational analyses and resulted in exclusion from the per protocol analysis.

Patient replacement and missing data

Main clinical outcome

For participants with missing values for the main clinical outcome (PDQ-39), three approaches were used:

I - In case only the 12-month follow-up PDQ-39 was missing and the 9-month PDQ-39 was present, the latter was used, minus or plus the mean difference in PDQ-39 between nine and 12 months follow-up for that treatment arm (of present data), since little change in PDQ-39 between nine and 12 months follow-up was expected.

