II - In case both follow-up PDQ-39's were missing (*i.e.*, nine and 12 months) but a baseline PDQ-39 was available, multiple imputation was used by fully conditional specification using predictive mean matching with five data sets and with potentially relevant variables at baseline (*e.g.*, age, sex, PDQ-39), previously observed outcomes and adverse events as predictors. The predictive mean matching imputation was performed separately per treatment group of the mITT population and chosen to ensure that imputed values were in the appropriate range.¹⁸ Additionally, we repeated this imputation of the PDQ-39 for the total mITT population as a scenario analysis.

III - For patients with a missing baseline PDQ-39, the imputation method as described in II was used, with follow-up PDQ-39 score(s) as covariate(s).

Since missing values were expected to be missing not at random, a conformity scenario and multiple worst-case scenarios for the mITT analysis were predefined, making use of additionally gathered data if possible. If lost to follow-up, the patients' treating physicians were asked to provide information on these patients regarding their treatment and functioning at 12 months after start of the allocated treatment (*i.e.*, deceased and if so, cause of death; use of the allocated treatment; use of the alternative than allocated treatment; living at home or in a health care facility; and modified Rankin scale).¹⁹ Loss to follow-up because of clinical improvement was deemed unlikely, therefore the conformity scenario for a patient with a missing 12-month PDQ-39 summary index score was to assign the mean PDQ-39 value in the allocated treatment arm. Possible worst-case scenarios were: (A) to assign the lowest assessed PDQ-39 in both treatment arms, and (B) scenario 1 minus ½ minimal clinically important difference (*i.e.*, ½ of -1,6 as defined in literature).²⁰ Based on the additional data acquired in case of loss to follow-up, the most applicable worst-case scenario was selected and justified.

In case of death, the 9-month follow-up PDQ-39 was carried forward if available. For patients alive at the moment of the 9-month follow-up, but without available PDQ-39 at that moment, the 9-month imputed PDQ-39 was carried forward. In case of death before the 9-month follow-up time point, no PDQ-39 summary index scores were used for this patient.

Secondary outcomes

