For normally distributed data means and standard deviation were presented, for non-normally distributed data medians and interquartile ranges. For the Hoehn & Yahr stage median and range were reported.

Analyses

Randomized controlled trial

Reported outcomes were presented in Table SAP2 (part A and B). The main publication consisted of analyses in the mITT population. The analyses in ITT, as-treated and per-protocol populations were presented in supplements.

Analysis of main clinical outcome

The main analysis regarding the clinical outcome was the between-group difference in change from baseline to 12 months follow-up in total PDQ-39 summary index score in the mITT population, using a two-group *t*-test. Additionally, a multiple linear regression analysis was performed taking into account the stratifying variable (level of experience of the treatment center) and (if necessary) clinically relevant baseline imbalances. To assess whether the baseline value of the PDQ-39 served as an effect modifier (meaning that the association between intervention and outcome differed according to baseline PDQ-39) an interaction term was used in the regression analysis. In case of a significant interaction term, the analysis was additionally performed in two separate strata: one with patients with a median PDQ-39 or below and the other with patients with a PDQ-39 above median.

Sensitivity analyses

Sensitivity analyses concerning missing data as described in the paragraph “Patient replacement and missing data” were performed in the mITT population. To further assess robustness of the mITT analysis for the main clinical outcome additional sensitivity analyses were performed.

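### PDQ-39 missing data: five imputed data sets leave the result dependent on the random seed, and the single-value month-9 fill makes the standard error slightly too small

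*SAP*

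**What the plan says.** The SAP section on patient replacement and missing data sets out three approaches for the main clinical outcome.

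- **Approach I** applies when month 12 is missing and month 9 is present. The month-9 score is used, "minus or plus the mean difference in PDQ-39 between nine and 12 months follow-up for that treatment arm", with the reason "since little change in PDQ-39 between nine and 12 months follow-up was expected". No residual variation is added.
- **Approach II** ("In case both follow-up PDQ-39's were missing", with baseline available) is multiple imputation "using predictive mean matching with five data sets". On the model, the SAP says: "The predictive mean matching imputation was performed separately per treatment group of the mITT population". Imputation with both arms pooled is a scenario analysis.
- **Approach III** applies the method of II to a missing baseline score.

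The completed data feed a two-group t-test of the "between-group difference in change from baseline to 12 months follow-up in total PDQ-39 summary index score in the mITT population". Under General principles this is the only clinical outcome judged at two-sided P<0.05. The health economics plan (Handling of missing data) carries the same PDQ-39 handling into the cost-effectiveness analysis.

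The SAP names no pooling rule and no seed, and does not say how many patients fall under each approach. Its synopsis of protocol development notes that "up to 2016 the nine months visits proved incomplete with regard to the PDQ-39 assessments".

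**The concern.** The two approaches raise different problems.

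Under approach II the estimate is an average over random draws. With few draws, a second run with another seed gives a noticeably different estimate and P-value. That matters most for a result near 0.05.

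Under approach I every filled score enters the t-test as if it had been measured. How far individual patients vary between months 9 and 12 is ignored, and so is the uncertainty in the arm's mean shift, so the SE is too small. Incomplete month-9 data cut both ways here: fewer patients can be filled, but the shift is estimated from fewer patients.

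**Working it through.** **Plan's own figures.** Protocol 4.4 gives a QALY SD of 0.35, a cost SD of €10,000, a willingness to pay of €120,000 and a difference of 0.2847 QALY. The SD on the net-benefit scale is sqrt(0.35² + (10,000/120,000)²) = 0.3598. This gives 26 per group (power 79.9%), and 26/0.8 = 32.5, so 33 per group. With SD 15 and 26 per group the detectable PDQ-39 difference is 11.89; the protocol states 11.9. The plan's figures reproduce. It gives no figure for imputation error.

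**Inputs.** From the documents: 33 per arm, PDQ-39 SD 15, m = 5. Assumed, because the documents do not give them:
- between-imputation share λ of 0.05 to 0.3;
- month 9 to 12 correlation ρ of 0.7 to 0.9;
- share f of each arm filled by approach I of 3% to 20%;
- baseline correlation 0.5, which makes the SD of change 15 × sqrt(2 × 0.5) = 15.

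The sampling SE of the difference is 15 × sqrt(2/33) = 3.69 points (4.16 at 26 per arm).

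**Approach II: Monte Carlo error.** With B the between-imputation variance and T the total variance, the Monte Carlo SE is sqrt(B/m) with B = λT/(1 + 1/m). As a fraction of the sampling SE this is sqrt(λ/(m + 1)).

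| λ | m = 5, points (fraction of SE) | m = 50, points (fraction of SE) |
|---|---|---|
| 0.05 | 0.34 (9%) | 0.12 (3%) |
| 0.1 | 0.48 (13%) | 0.16 (4%) |
| 0.2 | 0.67 (18%) | 0.23 (6%) |
| 0.3 | 0.83 (22%) | 0.28 (8%) |

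Take a result whose stable P is 0.05 (t about 2.00 on 60 df) and let only the estimate vary. At λ = 0.1, 95% of five-set runs fall at t = 2.00 ± 1.96 × 0.129, or P = 0.028 to 0.086. At λ = 0.3 the range is 0.018 to 0.124. With fifty sets the ranges are 0.041 to 0.060 and 0.036 to 0.069.

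**Approach II: interval width.** Under Rubin's rules the variance includes (1 + 1/m)B, so a small m cannot make the interval systematically narrow. With 7 of 33 per arm imputed (normal model), simulation gave coverage 95.2% and width 17.08 at m = 5, against 95.6% and 16.57 at m = 50.

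**Approach I: understated SE.** Write D for the month 9 to 12 change, with variance 2(1 − ρ)σ². After filling, the arm mean at month 12 equals the mean of all month-9 scores plus the mean D in patients with both visits. The covariance of D with the month-9 score is −(1 − ρ)σ². The true variance is therefore (σ²/n)[1 + 2(1 − ρ)f/(1 − f)], while the t-test uses about σ²/n. Example: ρ = 0.7 and f = 0.1 give 1 + 0.6 × 0.1/0.9 = 1.067, and 1 − 1/sqrt(1.067) = 3.2%.

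| Share filled | SE too small by (ρ 0.9 to 0.7) | Coverage of 95% interval |
|---|---|---|
| 3% | 0.3% to 0.9% | 94.9% to 94.8% |
| 10% | 1.1% to 3.2% | 94.7% to 94.2% |
| 20% | 2.4% to 6.7% | 94.4% to 93.2% |

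Simulation of the fill alone at ρ = 0.8 gave coverage of 94.8%, 94.4% and 93.7% with 1, 3 and 7 of 33 filled. At 26 per arm and ρ of 0.7 to 0.8, type I error was 5.6% to 6.0% with 3 filled per arm and 6.4% to 6.9% with 6.

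**Effect of the change.** With 3 filled and 4 imputed per arm (normal model), mean interval width was 15.89 for fixed fill with m = 5, 15.68 for fixed fill with m = 50, and 16.18 with all seven imputed at m = 50. Then 16.18/15.68 = 1.03. Under predictive mean matching with 5 donors (the SAP states no donor number), coverage was 94.1% for the SAP's scheme and 94.2% with all imputed at m = 50. The latter rests on 500 runs, with a simulation error of about 1 percentage point.

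**The case against.** The strongest reply is that both effects are small and their upper ends cannot occur together. In a normal-model simulation imputing from baseline, λ was 0.10 with 4 of 33 missing, 0.18 with 7 and 0.32 with 12. So λ = 0.3 needs about a third of each arm under approach II, while protocol 4.4 plans for 20% dropout in all, and patients who quit straight after randomisation are outside the mITT analysis. The same patients cannot also fill approach I. The loss of precision from m = 5 is slight: variance inflation 1 + λ/m is 1.01 to 1.06. Setting 0.3 to 0.8 points against the 1.6-point important difference cited in the SAP overstates the matter, since the sampling SE is about 3.7 to 4.2 points and the detectable difference 11.9. All of this stands, and it limits the size of the point.

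Other analyses are also planned. The as-treated analysis does not impute. A missed 12-month visit counts as a violation (SAP Appendix I) and so removes a patient from the per-protocol analysis. There are pooled-arm, conformity and worst-case scenarios. These would help to expose a result driven by imputation, but each also changes the population or the missing-data assumption. None varies the number of data sets or isolates the fill.

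A reader might infer that five data sets make the confidence interval too narrow. The documents do not support that: only approach I narrows the interval. The SAP does not name Rubin's rules, but that is a gap in specification and not evidence of a wrong rule.

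**Conclusion.** The point holds as two modest and separate weaknesses in the main clinical analysis.

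1. Five data sets leave avoidable Monte Carlo error of about 0.3 to 0.8 points, against 0.1 to 0.3 with fifty, for λ of 0.05 to 0.3. Under 20% dropout, λ up to about 0.2 is the more credible part of that range. The consequence is a borderline P-value that may not reproduce.
2. The fixed month-9 fill makes the SE too small by about 0.3% to 3% when 3% to 10% of patients are filled, and by up to about 7% at 20%. With few fills or ρ = 0.9 the effect nearly vanishes.

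Both ranges rest on stated assumptions about missing shares and correlations. It would also be tempting to conclude that changing the imputation restores nominal coverage. Under predictive mean matching the gain is small and has not been shown. The firm gains are reproducibility and not counting filled values as observed. PDQ-39 is the main clinical outcome; the trial's primary outcomes are economic, although PDQ-39 feeds one of them.

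**What to change.** - Use at least 50 imputed data sets, with a fixed and reported seed, and state that results are pooled by Rubin's rules. Fifty is a judgement; it brings the Monte Carlo SE down to 3% to 8% of the sampling SE.
- Replace approach I: enter the 9-month PDQ-39 as a predictor in the multiple imputation already planned for II and III, for every patient with a missing 12-month score.
- Keep the present month-9 fill as a sensitivity analysis, and report how many patients per arm fall under each approach.

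The cost is a change of settings, minutes of computing and an interval about 3% wider. No new data are needed.
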